9.4 General Criteria for Discontinuation of Study Product

Participants may voluntarily discontinue one or both study products for any reason at any time. Site IoRs will temporarily hold or permanently discontinue participants from one or both study products per protocol for any of the specific criteria below, which may be further clarified in the SSP Manual. Site IoRs also may temporarily hold or permanently discontinue participants from one or both study products for use of prohibited medication (per Section 6.7.1), for reasons not shown here or in the SSP Manual, e.g., to protect participant safety and/or if participants are unable or unwilling to comply with study product use procedures. In such cases, the Site IoRs would temporarily hold product use and provide a written query with a request for permanent study product discontinuation to the PSRT for review. The PSRT will provide a written response to the site indicating whether the PSRT has recommended permanent discontinuation of study product(s). Such recommendations regarding permanent discontinuation of one or both study products in individual participants will be made by the PSRT based on careful review of all relevant data.

The criteria for permanent discontinuation of further study product use of one or both study products for an individual participant are:

- Study product-related toxicity requiring permanent discontinuation of study product(s) per Section 9 of this protocol
- Completion of regimen as defined in the protocol
- Request by participant to terminate study product(s)
- Clinical reasons determined by the physician
- HIV infection
- Hepatitis B infection
- Pregnancy or breastfeeding

If a participant is permanently discontinued from oral study product, and if the Tenofovir 1% Gel Period has not yet begun for this participant, the investigator in consultation with the PSRT may decide that she may participate per protocol in the Tenofovir 1% Gel Period as scheduled according to her sequence randomization. If a participant is permanently discontinued from gel study product, and if the TDF 300 mg Oral Tablet Period has not yet begun for this participant, the investigator in consultation with the PSRT may decide that she may participate per protocol in the TDF 300 mg Oral Tablet Period has not yet begun for this participate per protocol in the TDF 300 mg Oral Tablet Period as scheduled according to her sequence randomization.

However, a participant who has been permanently discontinued from either type of study product will not take any study product during the Dual Formulation Period (if this study period has not yet begun for an individual participant), but will be followed according to regularly scheduled evaluations of safety, according to Section 7.4.5.

Participants may initiate study product use per protocol in a subsequent study period (if applicable), provided other product hold guidelines do not apply. Participants must meet applicable criteria for restarting a particular study product before initiating that study product's use in a subsequent study period.

9.5 Management of Specific Toxicities

Specific guidance related to product hold is also noted here as it pertains to the clinical management of toxicities.

9.5.1 Nausea and Vomiting

Participants with Grade 1 and/or 2 nausea or vomiting may be treated symptomatically with hydration, oral antiemetic therapies or antiemetic suppositories. Participants should be instructed to take oral study product with food.

ORAL STUDY PRODUCT

Participants with Grade \geq 3 nausea and/or vomiting must hold the study product until the toxicity grade returns to Grade \leq 2 and be treated symptomatically. Therapy should be resumed using the full doses of study product. If Grade \geq 3 nausea and/or vomiting recurs upon the resumption of study product despite symptomatic treatment, study product must be permanently discontinued.

VAGINAL STUDY PRODUCT

Unless other product hold guidelines apply, vaginal study product may be continued at the discretion of the investigator.

9.5.2 Diarrhea

Participants with diarrhea of any toxicity grade may be treated symptomatically with permitted antimotility agents and rehydration at the discretion of the site investigator.

ORAL STUDY PRODUCT

Participants with new onset Grade \geq 3 diarrhea that is unresponsive to antimotility agents and for which an alternative etiology (e.g., infectious diarrhea) is not established must hold the oral study product until the toxicity grade returns to Grade \leq 2 or to baseline and be treated symptomatically. Oral study product administration should be resumed using the full dose of oral study product. If Grade \geq 3 diarrhea recurs upon the resumption of oral study product despite symptomatic treatment, oral study product must be permanently discontinued.

VAGINAL STUDY PRODUCT

Unless other product hold guidelines apply, vaginal study product may be continued at the discretion of the investigator.

9.5.3 AST/ALT Elevations

Careful assessments should be done to rule out the use of alcohol, non-study medication-related drug toxicity, or viral hepatitis as the cause of elevation in AST or ALT of any grade.

ORAL STUDY PRODUCT

The participant must be carefully assessed for any symptoms or signs of hepatotoxicity, including fatigue, malaise, anorexia and nausea, jaundice, acholic stools, RUQ pain or hepatomegaly. If the AST/ALT elevation is considered most likely to be due to concomitant illness or medication, standard management, including discontinuation of the likely causative agent, should be undertaken.

If symptoms or signs of clinical hepatitis are present, study treatment must be discontinued (see below). Careful assessments should be undertaken for alcohol use, non-study medication-related drug toxicity, the lactic acidosis syndrome, and viral hepatitis as the cause of the transaminase elevation. If the AST/ALT elevation is considered most likely to be due to concomitant illness or medication, standard management, including discontinuation of the likely causative agent, should be undertaken.

Grade 1

For study participants with Grade 0 ALT and AST at study entry, an increase to Grade 1 ALT or AST even in an asymptomatic participant may be of concern.

ALT and AST must be repeated as soon as possible (at most within 1 week) of a new Grade 1 ALT or AST. Study treatment may be continued while repeating ALT and AST at the discretion of the investigator provided the participant is asymptomatic.

Participants with a confirmed Grade 1 ALT or AST who are asymptomatic may continue study medications with continued close observation.

Grade 2

Participants should have ALT/AST re-checked as soon as possible (at most within 1 week) and then be followed weekly until levels are Grade \leq 1. The frequency of follow up may be altered at the discretion of the site investigator following consultation with the PSRT. Study treatment may continue at the discretion of the investigator provided the participant is asymptomatic.

Grade 3

Study product should be held for any ALT or AST of Grade 3.

Participants should have ALT/AST re-checked as soon as possible (at most within 1 week). Participants should then be followed weekly until levels are Grade \leq 1, at which point study medication may be restarted with close follow-up and in consultation with

the PSRT. If lab documentation is not available that levels have returned to Grade ≤ 1 within three weeks, study product must be permanently discontinued.

For participants who have restarted study product, any level of Grade 3 or above should result in permanent discontinuation of study product.

Grade 4

Study product should be permanently discontinued. ALT/AST must be followed at least weekly until Grade ≤1.

VAGINAL STUDY PRODUCT

Unless other product hold guidelines apply, vaginal study product may be continued at the discretion of the investigator.

9.5.4 Creatinine Clearance

If the creatinine clearance is <50mL/min, it should be confirmed within 1 week of the receipt of the results in consultation with the PSRT.

ORAL STUDY PRODUCT

If the creatinine clearance is confirmed to be <50mL/min, the oral study product must be permanently discontinued. If the participant fails to have the creatinine clearance confirmed in one week, all attempts should be made by the site to contact the participant to have the creatinine clearance confirmed within three working days. Participants who fail to have a confirmed test will permanently discontinue the oral study product.

VAGINAL STUDY PRODUCT

Unless other product hold guidelines apply, vaginal study product may be continued at the discretion of the investigator.

9.5.5 Hypophosphatemia

For Grades 1 and 2 hypophosphatemia, the phosphate should be repeated within 2 weeks of the receipt of the results. Supplemental phosphate should be given with phosphate-rich food or fluid with or without neutral phosphate solution. For Grades 3 and 4 hypophosphatemia, the phosphate should be repeated within 1 week of the receipt of the results. Supplemental phosphate should be given with phosphate-rich food or fluid with or without neutral phosphate solution, and other causes of low phosphate should be investigated. During the time that supplemental phosphate is provided to the participant and the time that testing is repeated, sites should follow product hold guidelines described in Section 9.3.

ORAL STUDY PRODUCT

If documentation is not available within 1 week to show response to supplementation (resolution to Grade \leq 2), the oral study product must be permanently discontinued.

VAGINAL STUDY PRODUCT

Unless other product hold guidelines apply, vaginal study product may be continued at the discretion of the investigator.

9.5.6 Genital Sexually Transmitted Infection/Reproductive Tract Infection

Management of sexually transmitted infections commonly referred to as STIs and other forms of vaginitis and cervicitis will be in accordance with current WHO guidelines, available at http://www.who.int/en/.

ORAL STUDY PRODUCT:

Oral study product need not be held in the event of genital STI/RTI requiring treatment, unless other product hold guidelines apply.

VAGINAL STUDY PRODUCT

For Grade 2 genital STI(s)/RTI(s) requiring treatment, vaginal study product may be held until treatment is completed and symptoms have resolved at the judgment of the investigator. Once treatment is complete and any symptoms have resolved, vaginal study product use can be resumed unless other product hold guidelines apply.

9.6 HIV and Hepatitis B

Participants who are identified as infected with HIV and/or hepatitis B will be managed or referred for management according to the local standard of care. For additional guidance regarding participants who are identified as infected with HIV, please see Section 13.9.2.

NOTE: Participants who are identified as infected with HIV and/or hepatitis B will discontinue permanently all study product(s).

9.7 Clinical Management of Pregnancy

All study participants are required to be using an effective method of contraception according to Section 5.2 at enrollment, and intending to use same method for the duration of study participation. Study staff will provide contraceptive counseling to enrolled participants as needed throughout the duration of study participation and will facilitate access to contraceptive services through direct service delivery and/or active referrals to local service providers. Study staff also will provide participants with male condoms and counseling on use of condoms ideally during every sex act during study participation.

Pregnancy testing will be performed at all study visits and participants will be encouraged to report all signs or symptoms of pregnancy to study staff. The site IoR or designee will counsel any participants who become pregnant regarding possible risks to the fetus according to site-specific SOPs. The IoR or designee also will refer the participant to all applicable services; however, sites will not be responsible for paying for pregnancy-related care.

Participants who are pregnant at the termination visit will continue to be followed until the pregnancy outcome is ascertained (or, in consultation with the PSRT, it is determined that the pregnancy outcome cannot be ascertained). Pregnancy outcomes will be reported on relevant case report forms; outcomes meeting criteria for EAE reporting also will be reported on EAE forms.

NOTE: Participants who become pregnant during the course of the study will discontinue permanently all study product(s).

9.8 Criteria for Early Termination of Study Participation

Participants may voluntarily withdraw from the study for any reason at any time. Site loRs may, with the approval of the PSRT, withdraw participants before their scheduled termination visit to protect their safety, and/or if participants are unable or unwilling to comply with study procedures. Participants also may be withdrawn if the study sponsors, government or regulatory authorities (including the Office of Human Research Protections (OHRP)), or site IRBs/ECs terminate the study prior to its planned end date. Site investigators are required to consult the Protocol Chair and Protocol Biostatistician prior to the termination of any study participant. Study staff will record the reason(s) for all withdrawals in participants' study records. In the event that participants who voluntarily withdraw from the study wish to re-join the study during their planned 21-week follow-up period, they may resume study procedures and follow-up at the investigator's discretion.

10 STATISTICAL CONSIDERATIONS

10.1 Overview and General Design

This is a three-period, three treatment, multi-site, open label, crossover study. All the enrolled women will use all three treatments (i.e. oral TDF, tenofovir 1% gel, and a period of using both products), each in a separate period. The sequence of the three treatments will be randomly assigned. The total length of follow-up is 21 weeks: three periods of 6 weeks on treatment, each followed by a one-week washout period.

Each one-week washout period will be used to collect adverse events that may have resulted from product use during the previous period.

10.2 Study Endpoints

10.2.1 Study Primary Endpoints

Consistent with the primary study objectives, the following primary endpoints will be assessed:

- Adherence. Participant self reported product use. For each woman, adherence to each regimen will be computed by dividing the number of daily doses she reports having taken (numerator) by the number of expected doses if she were fully adherent (denominator).
- **Acceptability.** The proportion of participants who indicate that they would be "unlikely" to use the study product in the future.
- **PK.** AUC, C_{max}, and C_{min} associated with oral, vaginal, and dual use regimens.

10.2.2 Study Secondary Endpoints

Consistent with the secondary study objectives, the following secondary endpoints will be assessed:

- Proportion of women who report taking at least 90% of expected daily doses, frequency of use during the follow-up interval using an ordinal measure (5 categories of use, never to always); number of days product missed or not used during the previous week
- Frequency (ordinal measures) of sexual activity and male condom use
- Time interval between product usage and sexual intercourse; sequence of product use and sexual intercourse
- Reported sharing of study product; quantity of shared study product
- Grade 3 or higher toxicity for systemic and local effects as defined by DAIDS AE Grading Table Version 1.0, December 2004, or Grade 3 or higher genital infection, pain or epithelial lesion as defined by the Female Genital Grading Table for Use in Microbicide Studies which cannot be directly attributed to another cause, and judged as definitely, probably, possibly, or probably not related to the study gel, applicator, or study tablet

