A Phase 2 study of tenofovir 1% gel (HPTN 059) has completed follow up. This study assessed safety and acceptability of, and adherence to a regimen of tenofovir gel for vaginal use in HIV-uninfected women versus a placebo gel. Exploratory objectives included measurement of vaginal flora characteristics, assessment of the effects of gel on genital cytokine and chemokine expression, and the evaluation of cytokine and chemokine expression with evidence of inflammation, epithelial disruption and genital symptoms. The study was a Phase 2 four arm, three site, randomized, controlled trial comparing gel used once daily and gel used prior to intercourse, to placebo gel, with 6 months gel exposure and follow-up. The study was conducted among 200 women in Pune, India; Birmingham, Alabama, USA; and New York, New York, USA. Participants were sexually active, HIV-uninfected women between ages 18 and 50, but not menopausal or post menopausal. Participants had six months of study gel exposure and six months of follow-up. They were randomized to either once daily or coitally dependent group, and received either tenofovir or placebo gel. Participants received single use unit dose tubes and single use applicators.

No statistically significant differences were seen between those receiving active and placebo gels in complete blood count, liver function tests, or renal function tests. Among those using a study gel daily, no participants had pelvic exam findings involving

generalized erythema or severe edema or deep epithelial disruption at any follow-up visit during the study. At the Week 24 Visit, no participants had exam findings suggestive of vaginitis, cervicitis, superficial disruption, disrupted blood vessels, or intermenstrual bleeding. Adherence to study gel was high, and was supported by PK data. 79% of women reporting gel use in past 12 hours had low but detectable plasma tenofovir supporting self-reported adherence data. Daily and coital use was highly acceptable to women. These data suggest a favorable safety and acceptability profile of tenofovir gel, and support routine monitoring for genital findings among women without genital symptoms at six month intervals.¹⁰

Several other tenofovir gel studies are ongoing or in development. These include:

- CONRAD A04-095: Single Dose and 14-Day Once or Twice-daily Pharmacokinetic Study of the Vaginal Microbicide Agent 1% Tenofovir Gel (IND #73,382)

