Study site staff will report on study case report forms all AEs reported by or observed in enrolled study participants from the time of enrollment (random assignment) until study termination, regardless of severity and presumed relationship to study product. The Female Genital Grading Table for Use in Microbicide Studies (included in Appendix IV) will be the primary tool for grading adverse events for this protocol, with the exception of asymptomatic bacterial vaginosis which will not be a reportable AE. Adverse events not included in that table will be graded by the DAIDS AE Grading Table Version 1.0, December 2004. In cases where an AE is covered in both tables, the Female Genital Grading Table for Use in Microbicide Studies will be the grading scale utilized.

Participants will be encouraged to report to the study clinician any problems experienced by their male partners that might be potentially related to study product. If any such problems are reported, study staff should evaluate and document the occurrence and the Investigator of Record (or designee) should inform the PSRT, so that this information can be considered during routine PSRT safety data reviews. Should any concerns arise with regard to partner safety the PSRT will advise all study sites on appropriate action.

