¹ If pain or tendemess is included in the grading of another category (e.g., PID), it should not be graded again in the pain or tenderness category.

	INDIVIDUAL SIGNS/SYMPTOMS									
PARAMETER	GRADE 0 NORMAL	GRADE 1 MILD	GRADE 2 MODERATE	GRADE 3 SEVERE	GRADE 4 POTENTIALLY LIFE- THREATENING					
GENITOURINARY SIG	SNS/SYMPTOMS - V	/ULVA								
Vulvar/vaginal itching	None	Itching causing no, mild, or moderate interference with usual social & functional activities	Itching causing inability to perform usual social & functional activities; may require intervention such as antihistamine or bathing to provide relief	NA	NA					
Vulvar edema	None	Mild, non-pitting edema	Moderate, 1-2+ pitting edema	3+ pitting edema, severe enough to require urinary drainage, or weeping edema ± skin breakdown	NA					
Vulvar erythema	None	Erythema covering < 50% of vulvar surface	Erythema covering ≥ 50% of vulvar surface	NA	NA					
Vulvar lesions (findings seen only by colposcopy should not be included here)	Normal variants including skin tags, moles, scars, etc.	Blisters, ulcerations, or pustules - no treatment indicated	Blisters, ulcerations or pustules, with treatment indicated	Severe epithelial disruption with hospitalization indicated	NA					
Vulvar rash	None	Rash covering < 50% of vulvar surface	Rash covering ≥ 50% of vulvar surface	Severe epithelial disruption with hospitalization indicated	NA					
Bartholin's or Skene's gland	No findings	Cyst with no inflammation	Cyst or abscess with outpatient intervention indicated	Cyst or abscess with hospitalization indicated	Necrotizing fasciitis from Bartholin's abscess					
	GENITOURINARY SIGNS/SYMPTOMS – VAGINA ** Note – if vaginal discharge is present both by history and on examination, only report the one with the most severe grade									
Vaginal edema	None	Mild-moderate engorgement	Loss of ruggae and friability	NA	NA					

	INDIVIDUAL SIGNS/SYMPTOMS									
PARAMETER	GRADE 0 NORMAL	GRADE 1 MILD	GRADE 2 MODERATE	GRADE 3 SEVERE	GRADE 4 POTENTIALLY LIFE- THREATENING					
Vaginal erythema	None	Erythema covering < 50% of vaginal surface	Erythema covering ≥ 50% of vaginal surface	NA	NA					
Vaginal dryness	No complaint	Dryness causing no or minimal interference with usual sexual, social, & functional activities	Dryness causing greater than minimal interference with usual sexual, social, & functional activities	NA	NA					

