Menorrhagia ² (prolonged and/or heavy menstrual bleeding)	Participant report of normal bleeding relative to her baseline	Increase from usual with no or minimal interference with usual social & functional activities (including sexual functioning)	Increase from usual with moderate interference with usual social & functional activities (including sexual)	Incapacitating or severe interference with usual social & functional activities (including sexual functioning), transfusion indicated	Life threatening hemorrhage with or without shock
Metrorrhagia ² (intermenstrual or frequent bleeding)	None or any expected nonmenstrual bleeding	Increase from usual with no or minimal interference with usual social & functional activities (including sexual functioning)	Increase from usual with moderate interference with usual social & functional activities (including sexual)	Incapacitating or severe interference with usual social & functional activities (including sexual functioning), transfusion indicated	Life threatening hemorrhage with or without shock
Unexplained infrequent bleeding (excludes expected absence of menses due to hormonal contraception or pregnancy/postpartum)	Participant report of normal or expected bleeding frequency	No menses for 1-3 months (missed menses)	No menses for > 3 months (oligomenorrhea/ amenorrhea)	NA	NA
Postcoital bleeding	None	Occasional (< 25% of coital acts) OR Increase from usual with no or minimal interference with usual social functioning (including sexual functioning)	Frequent (25-75% of coital acts) OR Increase from usual with moderate interference with usual social functioning (including sexual)	Consistent (> 75% of coital acts) OR Incapacitating or severe interference with usual social functioning (including sexual functioning), transfusion indicated	Life threatening hemorrhage with or without shock

² If both Menorrhagia and Metrorrhagia are present, a single adverse event should be reported as "Menometrorrhagia" and graded per the Menorrhagia grading scale.

UTERINE BLEEDING AND PREGNANCY COMPLICATIONS					
PARAMETER	GRADE 0 NORMAL	GRADE 1 MILD	GRADE 2 MODERATE	GRADE 3 SEVERE	GRADE 4 POTENTIALLY LIFE- THREATENING
COMPLICATIONS OF	PREGNANCY				

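### The secondary safety endpoint does not fit the adverse event grading rule, so severe genital bleeding, hematuria and isolated severe vulvar edema fall outside both of its limbs or are left ambiguous

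*Protocol*

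**What the plan says.** Section 10.2.2, and the same item in the protocol summary, defines the safety endpoint by two alternatives. The first limb is "Grade 3 or higher toxicity for systemic and local effects as defined by DAIDS AE Grading Table Version 1.0, December 2004". The second is "Grade 3 or higher genital infection, pain or epithelial lesion as defined by the Female Genital Grading Table for Use in Microbicide Studies". An attribution condition then follows. This is the only endpoint listed for the secondary objective of characterizing the differential safety of the three regimens.

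The grading rule is in section 8.3.1 and is repeated in section 8.4 and Appendix IV. The Female Genital Grading Table is the primary tool. "Adverse events not included in that table will be graded by the DAIDS AE Grading Table Version 1.0, December 2004". For overlaps, "In cases where an AE is covered in both tables, the Female Genital Grading Table for Use in Microbicide Studies will be" the scale applied.

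Appendix IV reproduces the genital table. Menorrhagia and metrorrhagia have a Grade 3 cell reading "Incapacitating or severe interference with usual social & functional activities (including sexual functioning), transfusion indicated". Postcoital bleeding also has a Grade 3 cell, and all three rows have Grade 4 as "Life threatening hemorrhage with or without shock". Hematuria has Grade 3 and Grade 4 cells. Grade 3 vulvar edema is "3+ pitting edema, severe enough to require urinary drainage, or weeping edema ± skin breakdown".

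**The concern.** The second limb is narrower than the table it cites. The grading rule appears to close the other route into the endpoint, because an event listed in the genital table is graded there and so receives no DAIDS grade. A severe event of a type outside the three named ones then has nowhere to be counted, although the table defines Grade 3 or 4 for it.

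The comparison of regimens is at stake. Two of the three regimens include a vaginal product, and section 10.3 hypothesizes no adverse impact on the genital tract environment. If one regimen produced more severe genital bleeding than another, this endpoint, read literally, would not show it. This is separate from rows whose scale stops at Grade 2: the events here do have Grade 3 or 4 cells and drop out because of their type.

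**Working it through.** The plan states no figure to reproduce. The check sets the endpoint against the grading rule and then counts rows in Appendix IV.

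**Step 1: can the event enter through the first limb?** That limb requires Grade 3 or higher as defined by the DAIDS table. Section 8.3.1 uses the DAIDS table only for events absent from the genital table and gives the genital table priority in any overlap. Menorrhagia, metrorrhagia, postcoital bleeding, hematuria and vulvar edema are all rows of the genital table. Under the rule they have no DAIDS grade, whatever the DAIDS table contains.

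**Step 2: can it enter through the second limb?** This accepts infection, pain and epithelial lesion.
- Grade 4 postcoital bleeding, with no other finding: none of the three, not counted.
- Grade 3 vulvar edema with intact skin and no second sign: none of the three, not counted.
- Grade 3 vaginal laceration, for comparison: an epithelial lesion, counted.

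**Step 3: how much of the table is affected?** The base is every Appendix IV row outside the pregnancy complications with a Grade 3 or Grade 4 entry other than NA. There are 35, classified with a generous reading of the three types:
- Infection, 9: Bartholin's or Skene's gland, hydrosalpinx, pelvic inflammatory disease (two rows), herpes, chlamydia, gonorrhea, urinary tract infection, syphilis.
- Pain, 4: pain, tenderness, dysmenorrhea, dysuria.
- Epithelial lesion, 7: vulvar lesions, vulvar rash, vaginal abrasions or lacerations, vaginal lesions, condyloma, intraepithelial neoplasia, Pap.
- Disputable, 4: vulvovaginitis and cervicitis with no organism identified, two rows each.
- Not one of the three by name, 11: vulvar edema, menorrhagia, metrorrhagia, postcoital bleeding, hematuria and six mass rows.

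Check: 9 + 4 + 7 + 4 + 11 = 35.

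Four of the six mass rows name pain in their Grade 3 cell (vaginal and cervical, uterine, adnexal on bimanual exam, abdominal), so they could enter as pain. The other two (polyp, fibroid or thickened endometrium, and adnexal mass on ultrasound) do not. That leaves 11 − 4 = 7 rows, 7/35 = 20%. Without the two remaining mass rows there are 5 rows, 5/35 = 14%: three bleeding rows, hematuria and vulvar edema.

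**The case against.** The best counter-argument is that the first limb expressly covers local as well as systemic effects, has no restriction by type, and names its own grading source. Section 10.2.2 does not itself say that events in the genital table leave that limb; this follows only when it is combined with section 8.3.1. The DAIDS table is not reproduced, so its bleeding or edema entries cannot be checked. What stands is that the exclusion is inferred, so ambiguous wording is the safest minimum claim. The argument does not rescue the endpoint, because the reading needs a DAIDS grade that the grading rule denies to these events. Local effects still has a use under the rule, for local events that the genital table does not list.

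Some events would be captured another way. Appendix IV replaces individual categories by a composite one when two or more signs are present, so edema with a second sign such as pain or erythema may be graded as vulvovaginitis, one of the disputable rows. Edema with skin breakdown may be an epithelial lesion. Bleeding with a Grade 3 laceration counts through the laceration. The gap is therefore stated for isolated events.

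A reader might infer more than the documents support:
- *That these events are never counted.* Section 8.3.1 records all adverse events whatever their severity or relationship, and sections 8.1 and 8.2 provide regular safety review. The loss is confined to this endpoint.
- *That 11 of 35 rows (31%), or 15 of 35 (43%) with the disputable ones, are lost.* Four mass rows mention pain, and the disputable rows may count as infection.
- *That the omission favours the gel regimens.* No incidence is given, and section 2.6.1 lists hematuria among the frequent laboratory abnormalities in a study of oral TDF, so the gap is not purely on the gel side.
- *That the earlier Phase 2 gel study showed such harm.* Section 2.6.2 reports that no daily user had "generalized erythema or severe edema or deep epithelial disruption at any follow-up visit during the study", and that no participant had intermenstrual bleeding at Week 24. This shows what was assessed, not observed harm.

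A focus on infection, pain and epithelial damage could be deliberate, but nothing in the protocol says that a Grade 4 genital hemorrhage was meant to stay out.

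**Conclusion.** The concern holds as a mismatch between the endpoint's wording and the grading rule. Read together, they leave Grade 3 or 4 menorrhagia, metrorrhagia, postcoital bleeding and hematuria, and isolated Grade 3 vulvar edema without skin breakdown, in neither limb. Read more loosely, they leave it open whether these events count.

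The size is 5 to 7 of 35 rows, and the number of events cannot be derived from the protocol. The conclusion assumes that section 8.3.1 governs the grades used in section 10.2.2 and that the three named types carry their ordinary meaning. It affects the regimen comparison on a secondary endpoint, not the monitoring of participants, and probably few events, though severe ones. Because the endpoint is defined in the protocol itself, the correction belongs there.

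**What to change.** In the protocol summary and in section 10.2.2, replace the second limb with: *any Grade 3 or higher event as defined by the Female Genital Grading Table for Use in Microbicide Studies*. The first limb then covers events not in that table, in line with section 8.3.1. If some types are meant to stay out, for example masses, name them as exclusions. Leave the attribution wording unchanged.

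The cost is one phrase in two places. No new data are needed, since all adverse events are already collected and graded. The small downside is that some background events unrelated to product, such as masses or uterine bleeding, may be counted.
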